5.3 Safety Assessments

Safety assessments will include evaluation of the frequency and nature of adverse events (AEs) and adverse device effects (ADEs) up to 30 days after treatment application.

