6.4 Removal of Subjects from Study

In accordance with the current revision of the Declaration of Helsinki and the Code of Federal Regulations, a subject has the right to withdraw from the study at any time for any reason without prejudice to his/her future medical care by the physician or the institution. Should a subject (or subject's legally authorized guardian/representative) decide to withdraw; all efforts will be made to collect any adverse events they have experienced, if applicable. Subjects who withdraw or are terminated early from the study may be replaced. Participation may be terminated prior to completing the study for any of the reasons listed below (reasons that do not fit the categories below will be documented as "other").

Withdrawal of Consent:

If a subject chooses to withdraw early from the study, the eCRF completion page should be completed. When a subject's participation is terminated prior to completing the study, the reason for withdrawal is to be documented on the eCRF and in the source documentation.

Surgical:

The Investigator must withdraw a subject intraoperatively for the following reasons:

- Subjects do not have an appropriate target bleeding site.
- Subject develops coagulation diathesis post-operatively such as DIC (Disseminated Intravascular Coagulation).

Death:

When possible, the cause of death will be documented.

Lost to Follow-up:

All subjects should be encouraged to return for protocol required clinic visits for evaluation during the study follow-up period. If a patient is unable to return for a clinic visit or unable to be contacted by telephone, attempts to contact the patient should be documented in the source documents. Only after failing to contact the patient at the final follow-up visit, the patient will be considered lost to follow-up and the primary reason for early termination will be completed in the eCRF.

Site Termination or Study Termination:

The Sponsor may terminate a site or study at any time. When this occurs all subjects at the site will be withdrawn and documented as early termination. Reasons for site or study termination may include, but are not limited, to the following:

- Administrative concerns (e.g., inadequate patient enrollment, investigator/institution non-compliance, change of business strategy, etc.).

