- Safety issues, including reaching any of the complication thresholds, including those due to non-compliance, which substantially affect the risk-to-benefit ratio of the study subjects at a site or for the study as a whole.
- Futility: It is evident that the endpoint cannot be reached given the trial design and number of enrolled participants.
- Regulatory body mandates.

The Investigator has the right to terminate their participation at any time. Should this be necessary, procedures for termination will be provided by the Sponsor.

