9.8 Reporting Adverse Events

The Investigator is required to report all adverse events experienced by the patient from the day of the surgical procedure (Visit 2) until the patient completes Visit 3 (30 days after the surgical procedure) or withdraws early (prior to Visit 3). All adverse events (both serious and non-serious), regardless of their relatedness to the study device or procedure, must be reported in the Adverse Event eCRF. The investigator will evaluate the severity of the event, and its relatedness to the study device or procedure. Both severity and relatedness of all adverse events need to be entered in the Adverse Event eCRF.

Any necessary medical management of the event will be recorded in the patient's medical record/source document. All adverse events must be followed until resolution or until they become stable but ongoing.

The Investigator will record all adverse events (both serious and non-serious) in the source documents. Standard medical terminology should be used when recording adverse events. In addition, the following information should be recorded:

- Onset date
- Resolution date or date of death
- Severity of the event
- Action taken
- Event status (ongoing at study end or resolved)
- Relationship of adverse event to the device used in the study
- Relationship of the adverse event to the study surgical procedure
- Indication of whether the event is serious.

Data related to SAEs will be collected until event resolution, or until the event is considered stable, or until all attempts to determine the resolution of the event are exhausted. All adverse events that are unresolved at study completion (or early termination) will be recorded as ongoing at study end.

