9.8.2 Procedures for Reporting Unanticipated Adverse Device Effects

Reporting UADEs to the Sponsor

The study site must report all SAEs, whether they are related to the device or procedure, to the Sponsor as soon as possible, but no later than 24 hours of becoming aware of the SAE.

Information not available at the time of the initial report (e.g., an end date for the UADE) must be updated within the safety database. In the event of a fatal or life-threatening event, any required follow-up information must be submitted to the Sponsor immediately, but no later than 10 calendar days of the initial report.

If the Sponsor determines an UADE presents an unreasonable risk to subjects, the Sponsor shall terminate all or a portion of investigations as soon as possible so as not to jeopardize the health of any patient.

Termination shall occur no later than 5 working days after the Sponsor makes this determination and no later than 15 working days after the Sponsor first receives notice of effect. Resumption of terminated studies can occur only with IRB and FDA approval.

Reporting UADEs to the FDA

For any observed or volunteered adverse event that is determined to be a UADE, the sponsor-investigator will submit an expedited safety report to the FDA's Center for Devices and Radiological Health. The expedited safety report will consist of:

- a completed Form FDA 3500A
- a cover letter analyzing the significance of the event

A copy of this safety report will be provided to all participating study investigators.

The completed [Form FDA 3500A](#) and cover letter will be submitted to the FDA as soon as possible and, in no event, later than 10 working days after the sponsor-investigator first receives notice of the adverse effect.

If, following receipt and investigation of follow-up information regarding an adverse effect that was previously determined not to be a UADE, the sponsor-investigator determines that the event does meet the requirements for expedited reporting, the sponsor-investigator will submit a completed [Form FDA 3500A](#) and cover letter as soon as possible, but in no event later than 10 working days, after the determination is made.

Subsequent to the initial submission of a completed [FDA Form 3500A](#), the sponsor-investigator will submit additional information concerning the reported adverse effect as requested by the FDA.

Reporting Adverse Effects to the IRB

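### Terminating a site or the study withdraws subjects who are already treated, so those short of Visit 3 lose the scheduled Day 30 safety and re-bleeding follow-up

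*Combined protocol and SAP*

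**What the plan says.** Section 6.4 lets the sponsor terminate a site or the study at any time and states the consequence for subjects without qualification: "When this occurs all subjects at the site will be withdrawn and documented as early termination". The reasons listed there are administrative concerns, futility, regulatory mandate and safety, the last worded as "Safety issues, including reaching any of the complication thresholds, including those due to non-compliance, which substantially affect the risk-to-benefit ratio".

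Section 9.8 requires adverse event reporting from the day of surgery "until the patient completes Visit 3 (30 days after the surgical procedure) or withdraws early (prior to Visit 3").

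Section 9.8.2 deals with unanticipated adverse device effects (UADEs): "If the Sponsor determines an UADE presents an unreasonable risk to subjects, the Sponsor shall terminate all or a portion of investigations". It does not say what happens to subjects already treated. Section 14.6, the other termination section, asks only for written notification with the reason.

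Against this stands the planned follow-up, which section 5.3 counts from when the product is applied: "Safety assessments will include evaluation of the frequency and nature of adverse events (AEs) and adverse device effects (ADEs) up to 30 days after treatment". Section 7.3 has subjects monitored for re-bleeding from Day 0 to Day 30 and seen at Day 30 ± 7. Section 11.2.5 places postoperative re-bleeding requiring re-exploration, up to 30 days, fourth in the ordered list of secondary tests.

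**The concern.** A withdrawal rule in a drug trial may end exposure. Here each subject receives one application of an absorbable gauze during surgery. Once it is applied, withdrawing the subject from the study takes nothing away except study observation.

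The timing makes this worse. If the stop is for safety, the subjects still inside the 30-day window are those in whom the suspected problem could still appear, and their data are cut short because of the signal itself.

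If a single site is closed and the trial continues, the gap carries into the final analysis. Terminated subjects may be replaced (section 6.4), nothing is imputed for them (section 11.2.7), and their 30-day re-bleeding status is unknown for a tested secondary endpoint.

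**Working it through.** No figure in the plan is at stake, so the main check sets the passages side by side.

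**What termination does to a treated subject before Visit 3**

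1. Section 6.4: the subject is withdrawn and recorded as an early termination.
2. Section 9.8: routine adverse event reporting ends at Visit 3 or early withdrawal, whichever comes first.
3. Sections 5.3 and 7.3: the Day 30 visit, with its check for new events and for re-bleeding, is not kept for a withdrawn subject by any passage.

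**What still operates**

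- Section 6.4 on collecting events at withdrawal: "decide to withdraw; all efforts will be made to collect any adverse events they have experienced, if applicable". This concerns a subject's own decision and events that have already happened.
- Section 9.4: effects felt to be device-associated are followed until they resolve or stabilize.
- Section 9.8: known adverse events are followed to resolution or stability, although those unresolved at early termination are recorded as ongoing.
- Section 9.8.1: all serious events are collected through the follow-up visit, which a withdrawn subject does not have. After that visit, and after the study has concluded, serious events remain reportable within 24 hours if the investigator considers them related.
- Section 6.4 also promises sponsor procedures for termination, but for an investigator who ends participation. It sets no follow-up rule.

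What falls through is therefore new non-serious events, new serious events not judged related, and the scheduled re-bleeding and re-exploration assessment. The surviving routes are passive, and the one for new serious events depends on a causality judgement made in an open-label trial.

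**How many subjects**

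Inputs from the protocol: 236 randomized (section 11.1), 10 to 15 sites (synopsis), and a window of 30 days, or 37 at the upper limit of Visit 3. The accrual period is not given. I assume uniform accrual over 12 to 36 months of 30.4375 days.

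Subjects in the window = 236 / (months × 30.4375) × window in days.

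- 12 months: 236 / 365.25 = 0.646 per day; × 30 = 19.4; × 37 = 23.9.
- 24 months: 236 / 730.5 = 0.323 per day; × 30 = 9.7; × 37 = 12.0.
- 36 months: 236 / 1095.75 = 0.215 per day; × 30 = 6.5; × 37 = 8.0.

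Study-wide this is about 6 to 24 subjects. Per site with the 37-day window, the extremes are 23.9 / 10 = 2.4 and 8.0 / 15 = 0.5.

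Under uniform accrual the subjects in the window are spread evenly over it, so the average loss is half: 15 of 30 days, or 18.5 of 37.

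**The case against.** The strongest counter-argument is that section 9.8 has the patient as the one who withdraws, and that section 6.4 elsewhere separates subjects who withdraw from those terminated early. On that reading, termination by the sponsor does not clearly end adverse event reporting. This has some force: no sentence orders event collection to stop. But section 6.4 itself describes subjects at a terminated site as withdrawn, and no passage keeps Visit 3 for them. The narrow reading leaves the plan silent where it should be explicit.

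Three stronger readings are tempting and should not be drawn.

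- A reader might infer that all safety follow-up is lost. Sections 9.4, 9.8 and 9.8.1 do not support that. The loss is of scheduled, active study follow-up, and ordinary care is not touched.
- A reader might infer that a UADE-driven stop automatically withdraws every treated subject. Section 9.8.2 says "the Sponsor shall terminate all or a portion of investigations as soon as possible so as not to jeopardize the health of any patient". Ending a portion need not mean withdrawing treated subjects. The two sections leave open which route applies.
- A reader might divide 236 by 10 to 15 sites and take about 16 to 24 subjects per site as lost (236 / 15 = 15.7; 236 / 10 = 23.6). That is total enrolment per site. Those past Visit 3 have complete data.

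It is also fair to say that the safety analysis is descriptive (section 11.2.6), so the no-imputation rule matters less there, and that subjects past Visit 3 still inform the risk.

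**Conclusion.** The concern holds in limited form. Followed as written, sections 6.4 and 9.8 end active Day 30 event and re-bleeding collection in treated subjects whenever the sponsor terminates a site or the study, including for safety, and this serves no protective purpose because exposure is already complete.

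About 6 to 24 subjects would be affected at a study-wide stop, or 0.5 to 2.4 at a single site, each losing about half the window on average. Those counts rest on the assumed uniform accrual over 12 to 36 months and would change with the real rate. That the gap exists does not depend on them. The primary endpoint is observed within 10 minutes of application and is essentially unaffected. The plan should be corrected, but the point does not threaten the main comparison.

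**What to change.** Reconcile sections 6.4, 9.8, 9.8.1, 9.8.2 and 14.6 on whether active safety collection continues after termination.

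- **Section 6.4:** state that termination of a site or the study stops screening and randomization. Subjects already treated continue adverse event, serious adverse event and re-bleeding data collection through Visit 3, by telephone or through another site if theirs is closed. The exceptions are a subject who withdraws consent for follow-up and a contrary direction from a regulator or IRB. Only consented but untreated subjects are documented as early termination.
- **Section 9.8:** end adverse event reporting at Visit 3 or at withdrawal of consent for follow-up.
- **Sections 9.8.1, 9.8.2 and 14.6:** refer to the same rule.

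Collection by telephone or through another site also covers closure for non-compliance, where the site's own data collection may be the problem. The change concerns observation only, not clinical management.

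The cost is an amendment to wording. If a stop occurs, it adds one already planned visit or call per affected subject and a short hand-over or close-out period at a terminated site.

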7 STUDY PROCEDURES BY VISIT

Surgical procedures will be performed according to the expected standard of care and practices guided by the surgical specialty guidelines and institutional SOPs. Primary hemostasis of major bleeding should be achieved with conventional methods (i.e., clips, cautery, sutures). Subjects with an appropriate target bleeding site will allow the subject to be randomized into the study treatment. Each treatment will be applied in accordance with technical instructions provided in the investigator manual. Upon application of the study treatment at target bleeding site, a stopwatch will be started with inspection for bleeding occurring every 30 seconds for 10 minutes. In addition, the investigator will inspect the target bleeding site for 5 minutes after hemostasis is presumed to be achieved to ensure rebleeding does not occur.

All procedures will occur within the time windows defined in the study visit Schedule of Evaluations (see in [Table 1.1](#)).

7.1 Screening: Day -10 to Day 0 (Visit 1)

At the pre-operative visit, the physician will discuss with the patient the potential use of the investigational product, HemoStyp versus the standard of care product Surgicel, for secondary hemostasis. The physician performed the following procedures:

- Obtain written informed consent before any study-related procedures are conducted;
- Review of inclusion and exclusion criteria;
- Collect demographics data including age, sex, and race/ethnicity;
- Review medical history;
- Review and record concomitant medications (including any medication taken within 30 days of the screening visit);
- Record height and weight;
- Urine pregnancy test
- Measure vital signs (heart rate, respiratory rate, and blood pressure only);
- Laboratory tests (within 30 days prior to the screening visit). If these tests based on standard of care were done within 30 days prior to the screening visit date, these tests do not need to be repeated at the screening visit. The tests are, as follows:
 - Complete blood count (CBC), including hemoglobin, hematocrit, and platelet count; and
 - Coagulation tests, may include prothrombin (PT) and partial thromboplastin time (PTT) and International Normalized Ratio (INR) reflecting patients medical and medication history.

7.2 Study Treatment Day 0 (Visit 2 – Surgery)

On Day 1, eligible subjects will report to the hospital/surgical site at the scheduled time. Prior to surgery, the following procedures will be performed:

- Review of inclusion and exclusion criteria; and
- Review and record any changes to concomitant medications.

Other procedures will be performed in accordance with the pre-surgical and surgical site standards.

During the surgical procedure, subjects with appropriate target bleed sites (TBS) as determined using the validated bleeding severity scale (see [Section 8.6](#)) will be randomized to their assigned treatment (HemoStyp or Surgicel).

Each treatment will be applied in accordance with technical instructions provided in the investigator manual. Upon application of the study treatment at target bleeding site, a stopwatch will be started with inspection for bleeding occurring every 30 seconds for 10 minutes. In addition, the investigator will inspect the target bleeding site for 5 minutes after hemostasis is presumed to be achieved to ensure rebleeding does not occur.

7.3 Day 30 ± 7 (Visit 3)

From Day 0 through Day 30, subjects will be carefully monitored for any re-bleeding or need for exploratory surgery at the surgical site due to re-bleeding episodes. Any events of re-bleeding and/or requirement for additional surgery to address bleeding will be recorded and completely described.

On Day 30, subjects will report to the clinical for the follow-up procedures:

- Review and record concomitant medication;
- Assess for any re-bleeding at the target site; and
- Assess and record any adverse events or any adverse device reactions.

Following this, participation in the study will be completed.

8 STUDY PROCEDURES

8.1 Informed Consent

Adult Subjects

Each subject must sign and date a study specific ICF. The consent form will comply with all applicable regulations governing the protection of human subjects. An ICF approved by the Sponsor must be used.

The Investigator will obtain Institutional Review Board (IRB) written approval of the ICF to be provided to the subjects, including IRB approval of all revisions. Prior to entering the study, the Investigator or an authorized staff member will inform subjects about the nature of the study. Subjects will have the opportunity to inquire about details of the study and to decide whether to participate.

The Investigator will provide each subject with a copy of the signed and dated ICF and will document in the subject's source notes that informed consent was given.

8.2 Medical History

At the Screening Visit, a complete medical history will be obtained from each subject. The medical history will assess the subject for any disqualifying medical conditions as specified in the inclusion and exclusion criteria. The medical history will include all currently relevant history. When possible, only diagnoses and surgeries will be recorded. It is not necessary to collect history for remote, resolved conditions such as past pediatric illnesses or surgeries, unless the examining physician deems these conditions relevant.

8.3 Concomitant Medications

At the Screening and Randomization (Day 0) Visits, a list of all currently used medications will be obtained from each subject.

8.4 Height and Weight

The subject's height (cm or in) and weight (kg or lb) will be measured at the Screening Visit.

8.5 Vital Signs

Vital signs (heart rate, blood pressure, and temperature) will be assessed at the Screening Visit.

8.6 Laboratory Assessments

The investigator will review the laboratory report, document this review, and determine eligibility of the subject based on the laboratory findings.

8.7 Assessment of Target Bleeding Sites

During the surgical procedure on Day 1, appropriate target bleed sites will be identified, characterized, and recorded on the eCRF.

A specific bleeding area/site will be defined as the target bleeding site (TBS) when it is determined by the investigator that control of bleeding by conventional surgical techniques (including suture, ligature, and cautery) is ineffective or impractical and will require an adjunct treatment to achieve hemostasis. When the TBS is identified, the investigator will rate the intensity of the bleeding at the TBS according to the validated bleeding scale (Lewis 2017) shown in the table below. Only subjects with a TBS qualitative description of mild or moderate severity will be randomized.

The surgical raters used for intraoperative recruitment of patients will be trained on a video library of different bleeding rates. These videos will be verified with gravimetric measurements of blood loss. Inter- and Intra-rater reliability will be assessed prior to protocol participation. Inter- and Intra-rater concordance should exceed 90% for a bleeding grade of “0” or hemostasis and a bleeding grade of “3” or severe bleeding.

Validated Bleeding Severity Scale				
Grade	Visual presentation	Anatomic appearance	Qualitative description	Visually estimated rate of blood loss (mL/min)
0	No bleeding	No bleeding	No bleeding	≤1.0
1	Ooze or intermittent flow	Capillary-like bleeding	Mild	>1.0-5.0
2	Continuous flow	Venule and arteriolar-like bleeding	Moderate	>5.0-10.0
3	Controllable spurting and/or overwhelming flow	Noncentral venous- and arterial-like bleeding	Severe	>10.0-50.0
4	Unidentified or inaccessible spurting or gush	Central arterial- or venous-like bleeding	Life threatening*	>50.0

* Systemic resuscitation is required (e.g., volume expanders, vasopressors, blood products, etc.).
The scale is designed and validated for use in clinical studies to generate labeling claims. The scale is a Likert-type scale, in which the user assigns a grade based on the overall agreement of the items listed.
Source: Lewis 2017

Upon application of the study treatment at target bleeding site, a stopwatch will be started with inspection for bleeding occurring every 30 seconds for 10 minutes. In addition, the investigator will inspect the target bleeding site for 5 minutes after hemostasis is presumed to be achieved to ensure rebleeding does not occur. The source of the TBS will be identified and recorded as arterial, venous, or capillary.

